TRADIPITANT AMENDMENT NO. 2 TO PROTOCOL VP-VLY-686-1301

A SINGLE CENTER, RANDOMIZED, DOUBLE-BLIND, PLACEBO-CONTROLLED STUDY TO EVALUATE THE EFFECTS OF TRADIPITANT ON SATIATION, GASTRIC VOLUME, GASTRIC ACCOMODATION AND GASTRIC EMPTYING IN HEALTHY VOLUNTEERS

Author: [name].

[name]

Document Type: Clinical Study Protocol

Sponsor: Vanda Pharmaceuticals Inc.

[name]

[name]

[name]

USA

Principle Investigator: [name].

Co Investigators: [name] M.D., [name] M.D.

Study Product: tradipitant (VLY-686)

Protocol Number: VP-VLY-686-1301

Study Phase:

IND Number: 131545

Date: 10 May, 2021 **Status:** Final

Number of Pages: 68

SIGNATURE PAGE FOR VANDA PHARMACEUTICALS INC.

Amendment No. 2 to VP-VLY-686-1303

Approved by the following:

Program Lead:	[name]	5/14/2021 6:28 PM EDT
	[name].	Date
	Clinical Project Lead	
Medical Director:	[name]	5/21/2021 8:59 PM BST

[name].

Date

Medical Director

Name of Sponsor/Company:

Vanda Pharmaceuticals Inc.

Name of Investigational Product:

Tradipitant (VLY-686)

Name of Active Ingredient:

{2-[1-(3,5-Bistrifluoromethylbenzyl)-5-pyridin-4-yl-1H-[1,2,3]triazol-4-yl]-pyridin-3-yl}-(2-chlorophenyl)-methanone

Title of Study: VP-VLY-686-1301: A Single-Center, Placebo-Controlled, Double-Blind Study to Evaluate the Effects of Tradipitant on Satiation, Gastric Volume, Gastric Accommodation and Gastric Emptying in Healthy Volunteers

Study center(s): Clinical Enteric Neuroscience Translational and Epidemiological Research, Mayo Clinic, Rochester, MN

Indication: Healthy Volunteers Phase of development: I

Number of subjects (planned): Approximately 36 patients will be screened in order to fully complete the testing of 24 healthy subjects.

Inclusion Criteria:

- 1. Male and female subjects aged 18 65 years (inclusive);
- 2. No medical problems or chronic diseases, specifically, no type 2 diabetes mellitus.
- 3. Body Mass Index (BMI) of ≥ 18 and ≤ 35 kg/m² (BMI = weight (kg)/ [height (m)]²);
- 4. Subjects must agree to the following study restrictions:
- 5. Males of procreative capacity (not surgically sterile) will use an acceptable method of contraception from randomization through 1 month following the last dose of study medication. Examples of acceptable contraception for males include abstinence, use of a barrier method, or sterilized or post-menopausal partner;
- 6. Females of child-bearing potential (not surgically sterile or post-menopausal, defined as 12 months without menses) will use an acceptable method of contraception from 1 month prior to randomization (or screening, if earlier) through 1 month following the last dose of study medication. Examples of acceptable methods of contraception for females include abstinence, double barrier method, IUD, hormonal contraception, or sterilized partner;
- 7. Ability and acceptance to provide written informed consent;
- 8. Willing to participate in the pharmacogenomics sample collection;
- 9. Willing and able to comply with all study requirements and restrictions
- 10. Willing to not participate in any other interventional trial for the duration of their participation.

Exclusion Criteria:

- 11. Unable or unwilling to provide informed consent or to comply with study procedures.
- 12. Unwilling to agree to provide pharmacogenomics sample
- 13. Diagnosis of gastrointestinal diseases.
- 14. Structural or metabolic diseases that affect the GI system.

- 15. Unable to avoid the following over-the-counter medications 48 hours prior to the receipt of study medication and throughout the study:
- 16. Medications that alter GI transit including laxatives, magnesium and aluminum containing antacids, prokinetics, erythromycin;
- 17. Analgesic drugs including NSAIDs and COX-2 inhibitors

NOTE: Stable doses of thyroid replacement, estrogen replacement, low-dose aspirin for cardioprotection, and birth control are permissible.

- 18. History of recent surgery (within 60 days of screening).
- 19. Pregnant or nursing;
- 20. History of intolerance and/or hypersensitivity to medications similar to tradipitant and its accompanying excipients;
- 21. History (including family history) or current evidence of congenital long QT syndrome or known acquired QT interval prolongation (including QTcF > 450 in males or > 470 in females at screening);
- 22. History of suicide attempt and/or suicidal ideation (of type 4 or 5 on the Columbia Suicide Severity Rating Scale (C-SSRS)) within 2 years of screening or subject is at risk of suicide at Screening or Baseline visits, in the opinion of the investigator;
- 23. Recent history (within six months of screening) of Alcohol Use Disorder or Substance Use Disorder which may include a positive drug screen at the Screening visit;
- 24. Acute or chronic illness or history of illness, which in the opinion of the investigator could pose a threat or harm to the subject or obscure interpretation of laboratory test results or interpretation of study data such as frequent angina, Class III or IV congestive heart failure, any impairment of renal or hepatic function, poorly controlled diabetes, etc;
- 25. Indication of impaired liver function (including values for AST, ALT, or bilirubin > 2 times the Upper Limit of Normal, unless isolated bilirubin > 2 x ULN due solely to Gilbert's syndrome);
- 26. Has a creatinine level > 2x ULN;
- 27. Anyone affiliated as a member of the investigative team or sponsor and/or anyone who may consent under duress;
- 28. Any other reason as determined by the Investigator which may lead to an unfavorable risk-benefit of study participation, may interfere with study compliance, or may confound study results.

Investigational product, dosage and mode of administration:

Oral 85 mg tradipitant and matching placebo capsules will be administered from Mayo Research Pharmacy. Subjects will be randomized to one of two treatment arms to receive 85 mg tradipitant BID or placebo.

Duration of treatment:	Up to 9 days
Objectives:	
Primary:	

To evaluate the effects of tradipitant relative to placebo in healthy volunteers in the following:

- Difference in fasting GV
- Difference in postprandial GV and in accommodation volume (that is, postprandial minus fasting gastric volumes)
- Difference in gastric emptying ($T_{1/2}$, emptying at 2h and emptying at 4h)
- Volume to fullness (sensation of usual postprandial fullness) and maximum feeling of fullness (MTV).

Secondary:

- Absolute postprandial gastric volume
- Gastric volume (GV) ratio (postprandial/fasting GV)
- Gastric emptying of solids at 2h
- Gastric emptying of solids at 4h
- Intragastric meal distribution at time zero, (IMD⁰) following ingestion of test meal
- Maximum tolerated volume (MTV) during satiation test
- Aggregate symptoms score 30 min after MTV on satiation test
- Individual symptom scores (nausea, bloating, fullness, pain) on satiation test

Overall Design:

This is a randomized, double-blind, placebo-controlled, single center study during which healthy volunteers will be recruited, enrolled, and randomized to one of 2 treatment groups. Subjects meeting all inclusion/exclusion criteria will be randomized to either placebo or tradipitant, two 85mg tablet daily (b.i.d.) for 9 consecutive days. Subjects may be involved in study activity for up to five weeks from screening date to completion of all studies. The actual study related testing will be conducted on three days.

Enrollment of subjects will continue until N=24 of those that have been randomized to study medication and have completed all study testing through Day 9. Subjects who withdraw consent after being randomized will be included in an intent-to-treat analysis with missing data imputed based on data of completed subjects. Subjects that withdraw from participation before receipt of medication will be replaced. Subjects who have started their assigned study medication, but do not complete all the study testing through Day 9 will be replaced.

Primary Endpoint:

The primary objectives of this study are:

- Comparison of **fasting gastric volume** induced by tradipitant vs. placebo studied by single photon emission computed tomography (SPECT)
- Comparison of accommodation volume induced by tradipitant vs. placebo studied by SPECT
- Comparison of volume to fullness (VTF,mL) on **satiation test** for tradipitant vs. placebo
- Comparison of **gastric emptying** $T_{1/2}$ of solids on scintigraphy for tradipitant vs. placebo
- Comparison of gastric emptying values at 2 and 4 hours

Criteria for evaluation:

Efficacy:

- Single photon emission computed tomography (SPECT) to calculate fasting gastric volume and postprandial gastric accommodation
- Measurement of volume to fullness (mL) on satiation test
- Gastric emptying by scintigraphy

Safety:

- Safety and tolerability assessments will include the recording of adverse events (AEs), physical examinations, clinical laboratory evaluations, vital signs, and electrocardiograms.
- The Columbia-Suicide Severity Scale (C-SSRS) will be used to assess suicidal behavior and ideation.

Sample Size Discussion:

Sample size is based on the results of primary endpoints in the Mayo Clinic lab. Expected (80% power, α =0.05) demonstrable differences for tradipitant compared to placebo is 23.6% in the **gastric accommodation volume** and 29.2% in **gastric emptying** T1/2, based on the coefficients of variation observed from the Mayo Clinic laboratory in prior studies.

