11. STATISTICS

11.1. Sample Size and Accrual

Sample size assessment is based on the results of primary endpoints in the Mayo Clinic lab [data show mean \pm SD). Expected (80% power, α =0.05) demonstrable differences for tradipitant compared to placebo is 23.6% in the gastric accommodation volume and 29.2% in gastric emptying T1/2, based on the coefficients of variation observed from the Mayo Clinic laboratory in prior studies, as shown in the table below. [23] [24]

Table 7: Sample size and effect size estimates

Response	Mean	SD	Effect size detect-able,
			n=12/ group
Gastric accommodation,	507	100	119.7
mL			
GE solids t1/2 min	122	29.8	35.6

It is anticipated that all primary and secondary endpoints will be normally distributed. We shall use unpaired Student's t-test to compare study parameters between the placebo and Tradipitant groups. Covariate analysis may be conducted using gender and BMI as covariates, since these may significantly affect gastric functions such as satiation maximum tolerated volume.

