11.2.1. General

Statistical analyses will be performed using two-sided tests.

Data will be summarized by treatment group (and by visit when applicable), with respect to demographic and baseline characteristics, efficacy variables, and safety variables.

Summary statistics will include the mean, N, standard deviation, median, minimum, and maximum values for continuous variables, and frequencies and percentages for categorical variables.

Continuous efficacy variables will be analyzed using a mixed-effect model for repeated measures (MMRM) and/or an analysis of covariance (ANCOVA) model. The models will be described in the SAP.

For the analyses of change from baseline, only subjects with a baseline and at least one (1) post-baseline measure (GE, NDT, GA) will be included in the per protocol analysis. Unless otherwise

specified, baseline is defined as the latest non-missing observation across all the visits in the screening phase, before the active study drug begins. Endpoint will be the latest non-missing observation across all the post-baseline visits in the evaluation phase. A per protocol analysis of efficacy will be conducted using data actually collected and without any imputed data .

Categorical variables will be analyzed using the Cochran-Mantel-Haenszel (CMH) test blocking on sites, and Fisher's exact test will be used when site is not adjusted (mainly for safety assessment).

Details of the model and the analyses will be specified in the SAP. All statistical analyses will be performed using SAS®, Version 9.1.3 or higher.

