11.2.2. Subject Populations for Analysis

A subject will be defined as screened after the signature of the informed consent, regardless of the completion of all the screening procedures.

A subject will be defined as eligible if he/she meets all the inclusion/exclusion criteria. Otherwise he/she will be defined as a screen failure.

A subject will be defined as enrolled in the study if he/she is included into the evaluation phase of the study.

An eligible but not enrolled subject will be defined as a reserve.

The following analysis populations will be defined for this study:

Per protocol: will include any subject randomized into the study that receives a dose of study drug and that has completed at least one post-baseline efficacy measurement while on study medication;

Safety: Any subject randomized into the study that receives a dose of study drug;

Intent to Treat: Any subject who is randomized and receives the protocol required study drug exposure and required protocol processing.

Efficacy analyses will be performed on the Intent-to-Treat population and the Per-Protocol population. Safety summaries will be based on Safety set. Subject characteristics will be presented for all subjects randomized.

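### Consent withdrawals are imputed from completers on top of 24 observed completers, with no stated imputation method and a conflicting intent-to-treat definition

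*Protocol*

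**What the plan says.** Three rules stand together in the protocol synopsis, under Overall Design.

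- Accrual: "Enrollment of subjects will continue until N=24 of those that have been randomized to study medication and have completed all study testing".
- Replacement covers leaving before dosing ("Subjects that withdraw from participation before receipt of medication will be replaced") and leaving after it ("Subjects who have started their assigned study medication, but do not complete all the study testing through Day 9 will be replaced").
- Imputation: "Subjects who withdraw consent after being randomized will be included in an intent-to-treat analysis with missing data imputed based on data of completed subjects".

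SAP 11.1 gives the test: "We shall use unpaired Student's t-test to compare study parameters between the placebo and Tradipitant groups". SAP 11.2.1 also mentions a repeated-measures mixed model and/or analysis of covariance, and leaves the details to a later plan.

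On populations, SAP 11.2.2 defines intent-to-treat as: "Any subject who is randomized and receives the protocol required study drug exposure and required protocol processing". It then states: "Efficacy analyses will be performed on the Intent-to-Treat population and the Per-Protocol population". Neither is called primary. SAP 11.2.1 adds: "A per protocol analysis of efficacy will be conducted using data actually collected and without any imputed data".

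**The concern.** A subject who withdraws consent before finishing the tests is replaced, and is also kept in the intent-to-treat analysis with values taken from completers. Replacement has already secured the 12 observed subjects per group on which Table 7 rests. The imputed records therefore add to the count without adding information, and an ordinary t-test treats them as observations. A subject who leaves before the first dose has no on-treatment result at all, so every efficacy value would come from other people.

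The consequence depends on a method that is not stated. Filling once from the same arm makes the standard error too small. Filling once from all completers pooled pulls the arms together. Either way, withdrawals are assumed to resemble completers. That is open to doubt when the endpoints are gastric volumes, fullness and symptoms such as nausea and bloating, which may bear on the decision to leave.

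The two documents also disagree on whether these subjects enter the intent-to-treat comparison. With no primary population named, the choice could be made after the data are seen.

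**Working it through.** **Inputs.** SAP 11.1, Table 7: n = 12 per group; accommodation mean 507 mL, SD 100 mL, detectable difference 119.7 mL; solid emptying half-time mean 122 min, SD 29.8 min, detectable difference 35.6 min; 80% power, α = 0.05. SAP 11.2.1: two-sided tests. The number of filled subjects per arm, *m*, is an assumption (1 to 3). The 36 subjects to be screened do not give a withdrawal rate.

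**Step 1: the plan's own figures.** A two-sample t-test with 22 degrees of freedom (noncentral t, 80% power) gives a detectable difference of 119.68 mL (stated 119.7) and 35.66 min (stated 35.6). Relative differences: 119.7/507 = 23.6% and 35.6/122 = 29.2%. All reproduce, so the stated precision is that of 24 observed subjects.

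**Step 2: same-arm mean filled once.** The sum of squares is unchanged, but the variance is divided by 11 + m and the mean by 12 + m. Hence

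reported SE / correct SE = √[12 × 11 / ((12 + m)(11 + m))].

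The true two-sided error rate is the probability that |t| on 22 degrees of freedom exceeds this ratio times the 97.5% point of t on 2(12 + m) − 2 degrees of freedom.

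- m = 1: √(132/156) = 0.92; error rate 7.1%
- m = 2: √(132/182) = 0.85; error rate 9.4%
- m = 3: √(132/210) = 0.79; error rate 11.9%

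The treatment difference itself is not biased by this filling.

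**Step 3: pooled mean filled once.** Each arm mean becomes (12 × arm mean + m × pooled mean)/(12 + m), so the difference is multiplied by 12/(12 + m).

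- m = 1: 119.7 × 12/13 = 110.5 mL; 35.6 × 12/13 = 32.9 min
- m = 2: 119.7 × 12/14 = 102.6 mL; 35.6 × 12/14 = 30.5 min
- m = 3: 119.7 × 12/15 = 95.8 mL; 35.6 × 12/15 = 28.5 min

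The standard error shrinks in about the same proportion, so the error rate stays near 5% and power near 80%. The damage is to the estimate.

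**Step 4: other methods, by simulation.** Normal data, 12 completers plus m filled subjects per arm, true difference 1.197 SD for power. Single fills used 100,000 runs. Multiple imputation used 20,000 runs, 50 imputations, Rubin's rules and Barnard–Rubin degrees of freedom.

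| Method | Error rate, m = 1/2/3 | Power, m = 1/2/3 | Effect |
|---|---|---|---|
| One random same-arm value | 6.7 / 8.7 / 10.6% | 82 / 84 / 85% (inflated) | unbiased |
| One random pooled value | 5.0 / 5.0 / 5.0% | 76 / 71 / 68% | shrunk as in step 3 |
| Within-arm multiple imputation | 4.5 / 4.2 / 4.2% | 79 / 77 / 77% | undiluted |
| No imputed records | 5.0% | 80% | undiluted |

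Proper multiple imputation is safe, but it gains nothing over the 24 completers.

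**Step 5: the two intent-to-treat rules side by side.** The synopsis puts consent withdrawals into the intent-to-treat analysis. SAP 11.2.2 admits only subjects who had the required exposure and processing. A pre-dose withdrawal is in under the first and out under the second, and so are most other early withdrawals. Both rules cannot be followed.

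**The case against.** The strongest replies are these.

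- **Scope.** A reader might infer that every non-completer is both replaced and imputed. The text does not say so: imputation is stated only for consent withdrawals. A subject stopped for another reason is replaced, with no imputation mentioned, so the intolerance argument attaches to the rule only in part.
- **Method.** A reader might infer that the intent-to-treat result must be too precise or diluted. The wording is compatible with within-arm multiple imputation, which is neither, and SAP 11.2.1 leaves model details to a later plan. This stands. What remains is that neither document gives a method and the only test named in SAP 11.1 makes no allowance for imputed values.
- **The SAP definition may keep these subjects out.** True on a literal reading, but the synopsis includes them expressly. The statement that the per-protocol analysis has no imputed data suggests that another analysis does. This is a contradiction to resolve, not a safeguard.
- **An analysis without imputation is already planned.** True, and it limits the harm. The per-protocol set admits any dosed subject with at least one on-treatment efficacy measurement. It is not named as primary, however, so the imputed result could still lead.
- **Replacement plus retention is not an error in itself.** Correct. Replacement protects the number of completers, and retention respects randomization. The defect lies in the unspecified filling and the conflicting definitions.
- **Size.** Three withdrawals per arm would be 6 of 30 healthy volunteers (20%), which is high for up to 9 days of dosing. One per arm would be 2 of 26 (7.7%).

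**Conclusion.** The concern holds in a limited form. As written, the plan allows imputed records to be added to 24 observed completers and tested as if real, without saying how they are produced, and it contradicts itself on whether they enter. If values are filled once, one subject per arm is enough to move a nominal 5% test to about 7% (same-arm filling) or to cut the estimated difference to 92% of its true size (pooled filling). At three per arm the figures are about 11–12% and 80%.

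These sizes assume 12 completers per arm, equal numbers filled in each arm, normal data, a t-test on the filled data, and withdrawal unrelated to outcome. With no withdrawals there is no effect.

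A reader might also infer that dropping imputation removes bias from informative withdrawal. It does not. For a subject with no result, an observed-data analysis rests on essentially the same assumption as same-arm filling. What it removes is the false precision or the dilution.

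**What to change.** Replace the imputation sentence in the synopsis and the intent-to-treat definition in SAP 11.2.2 with one consistent rule, and name the primary analysis. Deleting the imputation phrase alone is not enough, because the synopsis would still require inclusion of subjects who may have no measurement.

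1. The primary efficacy analysis of each test uses every randomized subject with an observed on-treatment result for that test, in the assigned arm. This includes partial results from subjects later replaced, and no imputed values.
2. Any imputation is a sensitivity analysis, using multiple imputation within arm with Rubin's rules. Imputed subjects are not counted as added sample size.
3. Non-completers are reported by arm with reasons, as SAP 11.2.3 already plans. The report acknowledges that the observed-data analysis also assumes non-completers resemble completers.

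Cost: a wording change in both documents, with no added subjects or procedures. The small downside is that the number analysed for an endpoint may fall below the number randomized.

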11. STATISTICS

11.1. Sample Size and Accrual

Sample size assessment is based on the results of primary endpoints in the Mayo Clinic lab [data show mean \pm SD). Expected (80% power, α =0.05) demonstrable differences for tradipitant compared to placebo is 23.6% in the gastric accommodation volume and 29.2% in gastric emptying T1/2, based on the coefficients of variation observed from the Mayo Clinic laboratory in prior studies, as shown in the table below. [23] [24]

Table 7: Sample size and effect size estimates

Response	Mean	SD	Effect size detect-able,
			n=12/ group
Gastric accommodation,	507	100	119.7
mL			
GE solids t1/2 min	122	29.8	35.6

It is anticipated that all primary and secondary endpoints will be normally distributed. We shall use unpaired Student's t-test to compare study parameters between the placebo and Tradipitant groups. Covariate analysis may be conducted using gender and BMI as covariates, since these may significantly affect gastric functions such as satiation maximum tolerated volume.

11.2. Statistical Methods and Analysis Plan

This section describes the planned statistical analyses in general terms.

11.2.1. General

Statistical analyses will be performed using two-sided tests.

Data will be summarized by treatment group (and by visit when applicable), with respect to demographic and baseline characteristics, efficacy variables, and safety variables.

Summary statistics will include the mean, N, standard deviation, median, minimum, and maximum values for continuous variables, and frequencies and percentages for categorical variables.

Continuous efficacy variables will be analyzed using a mixed-effect model for repeated measures (MMRM) and/or an analysis of covariance (ANCOVA) model. The models will be described in the SAP.

For the analyses of change from baseline, only subjects with a baseline and at least one (1) post-baseline measure (GE, NDT, GA) will be included in the per protocol analysis. Unless otherwise

specified, baseline is defined as the latest non-missing observation across all the visits in the screening phase, before the active study drug begins. Endpoint will be the latest non-missing observation across all the post-baseline visits in the evaluation phase. A per protocol analysis of efficacy will be conducted using data actually collected and without any imputed data .

Categorical variables will be analyzed using the Cochran-Mantel-Haenszel (CMH) test blocking on sites, and Fisher's exact test will be used when site is not adjusted (mainly for safety assessment).

Details of the model and the analyses will be specified in the SAP. All statistical analyses will be performed using SAS®, Version 9.1.3 or higher.

